7.9 Patient Follow Up

All patients will need to be followed up for safety (AEs) up to 30 days (+/- 5 days) after the last dose of avelumab and for disease progression / survival until the end of the trial (minimum of 12 months follow-up from the date of commencing treatment for the last patient).

If the patient stops trial treatment but has not progressed, they will be reviewed with a CT scan of neck, chest, abdomen and pelvis at 8, 12, 16 and 20 months or on clinical suspicion of progression (whichever is sooner).

If there is no evidence of progression after 20 months, patients will have no specific trial follow up, but their referring physician may be contacted every 6 months to determine progression and survival data.

7.10 Patient Withdrawal of Consent

In the event of a patient's decision to withdraw from the trial, the Investigator should ascertain from which aspects of the trial the patient wishes to withdraw and record the details on the appropriate CRF. All information and blood/tissue samples collected up until point of retraction will be retained and analysed. If a patient chooses to withdraw from treatment only, the patient should discontinue treatment and continue to be assessed in accordance with the protocol. If a patient wishes to withdraw from the trial (i.e. including trial specific assessments), but is willing for further data to be supplied to the Trials Office, then further routine "follow-up" data (e.g. disease status and survival) will continue to be supplied by the Investigator to the Trials Office.

8. ADVERSE EVENT REPORTING

The collection and reporting of Adverse Events (AEs) will be in accordance with the Medicines for Human Use Clinical Trials Regulations 2004 and its subsequent amendments. Definitions of different types of AE are listed in Appendix 3. The Investigator should assess the seriousness and causality (relatedness) of all AEs experienced by the patient (this should be documented in the source data) with reference to the Investigator Brochure.

8.1 Reporting Requirements

8.1.1 Adverse Events

All medical occurrences which meet the definition of an AE (see Appendix 3 for definition) should be reported. Please note this does not include abnormal laboratory findings. An abnormal laboratory value is only considered to be an AE if the abnormality:

- Results in early discontinuation from the study treatment and/or
- Requires study drug dose modification or interruption, any other therapeutic intervention or is judged to be of significant clinical importance

If a laboratory abnormality is one component of a diagnosis or syndrome, then only the diagnosis or syndrome should be recorded.

Pre-existing conditions should only be reported if the condition worsens by at least 1 CTCAE grade. Details of all AEs experienced by the patient should be recorded in the hospital notes.

8.1.2 Serious Adverse Advents

Investigators should report AEs that meet the definition of an SAE (see Appendix 3 for definition) and are not excluded from the reporting process as described below.

Potential drug-induced liver injury (Hy's Law cases) are considered important medical events and should be reported as SAEs. Please see section 7 for more information.

8.1.2.1 Events that do not require reporting on a Serious Adverse Event Form

The following events should not be reported on an SAE Form and are not classed as SAEs for this trial:

- Hospitalisations for:
 - Pre-planned elective procedures unless the condition worsens
 - Treatment for progression of the patient's cancer
- Progression or death as a result of the patient's cancer, as this information is captured elsewhere on the Case Report Form

The below events may not be SAEs but should still be reported by email to the trials office within 24h of becoming aware of the event:

- Exposure during Pregnancy or Breastfeeding (even if not associated with an adverse event)
- Occupational exposure during the performance of job duties, a person (whether a healthcare professional or otherwise) gets in unplanned direct contact with the product (even if not associated with an adverse event)

Details of these will be forwarded to Pfizer for review.

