1.1 Background

Peripheral T-cell lymphomas (PTCLs) are a heterogeneous, often aggressive, group of non-Hodgkin lymphomas (NHL) comprising about 5% to 10% of all new NHL diagnoses. The most common subtypes are peripheral T-cell lymphoma not otherwise specified (PTCL-NOS), angioimmunoblastic T-cell lymphoma (AITL), and anaplastic large-cell lymphoma (ALCL). Recent advances in understanding normal T-cell biology together with gene expression and immunohistochemistry studies have suggested that a group of PTCL are derived from the CD4⁺ T-cell subset, follicular helper T-cells (Tfh), which are characterised by surface expression of PD-1 and inducible co-stimulator (ICOS) and nuclear expression of BCL6¹⁻⁴. The ligand of PD-1, PD-L1, is expressed on both lymphoma cells and stromal cells⁵. Historically the therapeutic approaches for PTCL have been derived from standard treatments for various subtypes of aggressive B-cell lymphoma. However, outcomes remain poor when these strategies are used in the management of PTCL, with 5-year overall survival (OS) ranging from 25 to 35% for the common subtypes and excluding ALK-positive ALCL⁶.

Four drugs have been approved by the US Food and Drug Administration (FDA) for treatment of relapsed PTCL: pralatrexate, romidepsin, brentuximab vedotin (approved for ALCL only), and belinostat. In the relapsed/refractory setting, rates of response to single-agent therapy with these drugs (other than use of brentuximab vedotin for ALCL) range from 20% to 35%⁷⁻¹⁰.

Several mechanistically based therapies are currently in clinical trials for T-cell lymphoma. In patients with ALK-positive ALCL there are efforts to study crizotinib, which has been approved for treatment of lung cancer harboring a translocation in the *ALK* gene. As ALK is constitutively expressed in a subset of patients with ALCL, this is an attractive therapeutic target. In small series of relapsed patients, response rates of 60% to 100% to crizotinib have been seen, including one study of 11 patients (9 with ALCL) showing an overall response rate (ORR) of 91%¹¹. Several other ALK inhibitors are also in development but primarily these agents are being investigated in lung cancer.

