1.2.3 Choice of treatment

Cross-linking of PD-1 has been shown to inhibit T-cells¹⁹ and this has prompted interest in perturbing PD-1/PD-L1 signaling in order to enhance T-cell anti-tumour activity in solid cancers^{20,21}. However, this model does not appear to explain PD-1/PD-L1 function in Tfh-cells, a CD4⁺ T-cell subset required for germinal centre formation, in part, by providing IL-4 and IL-21 to cause B-cell proliferation^{22,23}. Data from mice lacking PD-1 demonstrates important functions for this surface protein in T-cell differentiation^{24,25}. While the earlier study²⁴ demonstrated that PD-1 deficient animals had increased follicular T-cells there was a paradoxical lack of increased functions attributable to the Tfh subset. Subsequent work following identification of a repressive follicular T-cell subset (Tfr)²⁵ has provided a resolution for this problem: PD-1^{-/-} mice show increased numbers and functions of Tfr whilst Tfh are repressed. Interestingly, mice lacking the PD-1 ligand (PD-L1) demonstrated the same phenotype. This suggests that *in vivo* the PD-1/PD-L1 axis regulates the differentiation of follicular T-cells such that stimulation of PD1 drives Tfh differentiation whereas blockade of PD-1/PD-L1 produces a repressive and Tfr dominated environment.

PD-L1 is expressed on both tumour and stromal components of PTCL (Table 1)⁵ by immunohistochemistry, which is likely to underestimate patients for which the PD-1/PD-L1 axis is functionally important. Avelumab, in distinction from other therapeutic anti-PDL1 antibodies causes antibody dependent cellular cytotoxicity (ADCC)²⁶. Therefore, avelumab may deplete essential stromal components of the tumour microenvironment as well as causing apoptosis of lymphoma cells.

Table 1

Percentage of cases expressing PD-L1 on tumour cells and stroma in PTCL (from Wilcox et al.⁵). Cutaneous PTCL have been excluded from the data.

	Tumour PD-L1 (%)	Stroma PD-L1 (%)
PTCL-NOS	17	43
AITL	5	57
ALK+ ALCL	33	22
ALK-ALCL	15	35
Other	10	24

EMR 100070-001 is a study of avelumab in metastatic and locally recurrent solid tumours. None of the patients treated with doses up to 10 mg/kg experienced a dose limiting toxicity and this dose is, therefore, considered a safe and well-tolerated dose (Avelumab Investigators Brochure v4.0, February 2015).

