8.2.5 Data/Safety Committee

The independent Trial Safety Committee (TSC) will review all SAEs.

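### The exclusion of progression and cancer death from SAE reporting (8.1.2.1) has no exception for events judged possibly related to avelumab

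*Combined protocol and SAP*

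**What the plan says.** Section 8.1.2 makes the investigator's SAE duty conditional: events are reported if they meet the Appendix 3 definition "and are not excluded from the reporting process as described below". Section 8.1.2.1 then names the events that "should not be reported on an SAE Form and are not classed as SAEs for this trial". Two entries concern the lymphoma:

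- admission to hospital in order to treat progressive disease;
- "Progression or death as a result of the patient's cancer, as this information is captured elsewhere on the Case Report Form".

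The one qualifier in the list, about a worsening condition, belongs to pre-planned elective procedures. Neither lymphoma entry mentions relatedness to avelumab.

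The exclusion recurs in 8.1.3, where the AE reporting period leaves out the listed events, and in 8.2.1.2, where the site SAE procedure excepts the events of section 8.1. Separately, the opening of section 8 asks the investigator to assess seriousness and causality for every AE and to document this in the source data.

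**The concern.** Leaving progression out of SAE reporting is a common and defensible default in lymphoma. It avoids flooding the safety system with the natural course of the disease. The usual safeguard is to lift the exclusion when someone suspects the drug contributed, and that safeguard is missing here.

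Two features of this trial make the omission worth closing. First, avelumab acts on the PD-1/PD-L1 axis and the malignant cell is itself a T-cell. Section 1.1 attributes a follicular helper T-cell (Tfh) origin only to a group of PTCL, and 4.1 admits a range of histologies. Second, section 1.2.2 rests the single-arm design on the assumption that the safety profile seen in solid cancers will carry over to haematological malignancy. In solid cancers the tumour cell is not a T-cell, so those data say little about an effect of the drug on the tumour cell's own signalling.

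At stake is the handling of individual cases. If an investigator suspects that avelumab contributed to a progression, the protocol should say where that suspicion goes.

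**Working it through.** No arithmetic applies. The check follows one hypothetical event through the reporting chain: a progression, or a death from lymphoma, that the investigator judges possibly related to avelumab.

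1. **Causality at site (section 8, opening).** The investigator records the judgement in the source data. Nothing links it to the exclusion list.
2. **SAE status (8.1.2, 8.1.2.1).** The event is listed, so it is not classed as an SAE and no SAE Form is completed. Appendix 3 counts any event resulting in death as serious, with no cancer exception. But 8.1.2 makes the reporting duty subject to the exclusions, so Appendix 3 does not bring the event back.
3. **AE reporting and site procedure (8.1.3, 8.2.1.2).** Both repeat the exclusion.
4. **Central review (8.2.2).** The Clinical Coordinator's review of seriousness and causality begins on receipt of an SAE Form, and expectedness is assessed for SARs. With no form, neither happens.
5. **SAR and SUSAR status (8.2.2, Appendix 3).** A SAR must also be an SAE, and a SUSAR must also be a SAR. An event not classed as an SAE is neither.
6. **Onward reporting (8.2.3.1, 8.2.3.2, 8.2.6).** There is therefore no 7-day or 15-day SUSAR report to the regulator and ethics committee, no entry as a SAR in the annual report, and no 24-hour SAE report to the manufacturer.
7. **Committee event review (8.2.5).** "The independent Trial Safety Committee (TSC) will review all SAEs". The event is not an SAE and so is not in that review.

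Possible ways back into the chain:

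- **8.1.4 (post-study SUSARs)** covers SAEs that are possibly related and unexpected. It removes the time limit only, and its starting point is still an SAE.
- **8.2.3.4 (other safety issues)** requires notification once a significant safety issue has been identified. It does not say how a single suspected case would be recognised as one.
- **Table 4, hepatic AEs** asks for immediate notice to the Chief Investigator and trials office about liver function or liver involvement by lymphoma. It covers the liver only and is not SAE reporting.
- **7.5.3 and 7.5.6.** Tumour lysis syndrome is not on the exclusion list, and confirmed Hy's law cases must be reported as SAEs. Separately diagnosed complications like these remain reportable, but they are not the progression itself.

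Relatedness-based exceptions to the progression exclusion found anywhere in the document: none.

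**The case against.** The strongest reply is that the exclusion is deliberate and the information is not lost. Section 8.1.2.1 gives its reason, "as this information is captured elsewhere on the Case Report Form". Under 13.4 the TSC meets at six-monthly intervals to monitor all safety, futility and primary activity data. Under 12.3 it also monitors accumulating data regularly, and at the 15-patient look any decision rests on all outcomes. Progression and death dates feed PFS and OS (12.1.2), so early progression can be told apart from simple non-response. Section 7.8 requires treatment to stop at progression and the reason to be recorded. In an uncontrolled trial with frequent background progression, single-case causality judgements discriminate poorly, and aggregate review may be the better instrument.

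Most of this stands. The TSC is not blind to progression, and a reader who inferred that such events would reach it only as six-monthly activity data would be going beyond the text. But aggregate review does not replace a route for the case where an investigator has already formed a suspicion. The protocol asks for that judgement and then gives it nowhere to go.

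A second reply concerns the biology. A reader might pair the sentence "Cross-linking of PD-1 has been shown to inhibit T-cells" with a T-cell tumour and infer that the protocol itself points to accelerated lymphoma, or leaves the question open. It does not. Section 1.2.3 goes on to say that this model does not seem to account for PD-1 function in Tfh cells. It presents later mouse work as resolving the paradox, and adds antibody-dependent cytotoxicity as a further anti-tumour mechanism. No section names accelerated progression as a risk or reports a case. This objection is right. The point rests on the reporting rule, the T-cell origin of the tumour and the carried-over safety assumption, and not on any claim that avelumab speeds up the disease.

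**Conclusion.** The gap holds as a matter of text. Under 8.1.2.1 and the sections that repeat it, a progression, lymphoma death or hospitalisation for progression judged possibly related to avelumab gets no central causality or expectedness assessment, cannot become a SAR or SUSAR, and is not in the TSC's SAE review. This assumes sites follow the exclusion literally. An investigator could argue that a drug-driven event is not a result of the cancer, but no instruction says so.

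The size is modest and cannot be put as a number of patients. A reader might try to derive one from the median survival times in 1.2.3. That would count all expected deaths, whatever their cause, in a real-world cohort not selected for this trial, whereas 4.1 requires a life expectancy above 12 weeks. It would not measure drug-related events, for which the documents give no rate. Nor do they support calling accelerated progression the single serious risk particular to this tumour: tumour lysis (7.5.3) and hepatic involvement (4.1, Table 4) are the disease-linked hazards they name.

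The primary analysis is unaffected. This is an inexpensive improvement to safety reporting, not a defect in the trial's inference.

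**What to change.** 1. In 8.1.2.1, add that the exclusion of progression, death from the lymphoma and hospitalisation for progression does not apply when the investigator or the Clinical Coordinator judges the event at least possibly related to avelumab. Such an event is then an SAE and is assessed for expectedness.
2. Align 8.1.2, 8.1.3 and 8.2.1.2 so that their cross-references carry the same exception.
3. In 13.4, give the TSC a listing, drawn from existing CRF data, of progressions and deaths before the cycle 3 CT, at each meeting and at the 15-patient look. The Clinical Coordinator should receive it too, since that role otherwise sees only events that arrive on an SAE Form.

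The cost is protocol wording, one listing, and a few extra SAE forms and causality assessments. Events readmitted as SAEs would also count in the secondary toxicity outcome of 12.1.2, which includes SAEs of any grade, so the analysis text should say so. No treatment rule changes.

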8.1.2.2 Monitoring pregnancies for potential Serious Adverse Events

It is important to monitor the outcome of pregnancies of patients in order to provide SAE data on congenital anomalies or birth defects.

In the event that a patient or their partner becomes pregnant during the SAE reporting period please complete a Pregnancy Notification Form (providing the patient's details) and return to the Trials Office as soon as possible. If it is the patient who is pregnant provide outcome data on a follow-up Pregnancy Notification Form. Where the patient's partner is pregnant consent must first be obtained and the patient should be given a release of medical information form to give to their partner. If the partner is happy to provide information on the outcome of their pregnancy they should sign the release of medical information form. Once consent has been obtained provide details of the outcome of the pregnancy on a follow-up Pregnancy Notification Form. If appropriate also complete an SAE Form as detailed below.

8.1.3 Reporting period

Details of all AEs (except those listed above) will be documented and reported from the date of commencement of protocol defined treatment until 30 days after the administration of the last treatment.

8.1.4 Post study SUSARs

SAEs that are judged to be at least possibly related to the IMP(s) and are unexpected must still be reported in an expedited manner irrespective of how long after IMP administration the reaction occurred.

8.2 Reporting Procedure

8.2.1 Site

8.2.1.1 Adverse Events

AEs should be reported on an AE Form (and where applicable on an SAE Form). An AE Form should be completed at each visit and returned to the Trials Office.

AEs will be reviewed using the Common Terminology Criteria for Adverse Events (CTCAE), version 4.0 (see Appendix 4). Any AEs experienced by the patient but not included in the CTCAE should be graded by an Investigator and recorded on the AE Form using a scale of (1) mild, (2) moderate or (3) severe. For each sign/symptom, the highest grade observed since the last visit should be recorded.

8.2.1.2 Serious Adverse Events

For more detailed instructions on SAE reporting refer to the SAE Form Completion Guidelines contained in the Investigator Site File (ISF).

AEs defined as serious and which require reporting as an SAE (excluding events listed in Section 8.1 above) should be reported on an SAE Form. When completing the form, the Investigator will be asked to define the causality and the severity of the AE which should be documented using the CTCAE version 4.0.

On becoming aware that a patient has experienced an SAE, the Investigator (or delegate) must complete, date and sign an SAE Form. The form should be faxed together with a SAE Fax Cover Sheet to the Trials Office using one of the numbers listed below as soon as possible and no later than 24 hours after first becoming aware of the event:

To report an SAE, fax the SAE Form with an SAE Fax Cover Sheet to:

[name] or [name]

On receipt the Trials Office will allocate each SAE a unique reference number. This number will be transcribed onto the SAE Fax Cover Sheet which will then be faxed back to the site as proof of receipt. If confirmation of receipt is not received within 1 working day please contact the Trials Office. The SAE reference number should be quoted on all correspondence and follow-up reports regarding the SAE. The SAE Fax Cover Sheet completed by the Trials Office should be filed with the SAE Form in the ISF.

For SAE Forms completed by someone other than the Investigator the Investigator will be required to countersign the original SAE Form to confirm agreement with the causality and severity assessments. The form should then be returned to the Trials Office in the post and a copy kept in the ISF.

Investigators should also report SAEs to their own Trust in accordance with local practice.

8.2.1.3 Provision of follow-up information

Patients should be followed up until resolution or stabilisation of the event. Follow-up information should be provided on a new SAE Form (refer to the SAE Form Completion Guidelines for further information).

8.2.2 Trials Office

On receipt of an SAE Form seriousness and causality will be determined independently by a Clinical Coordinator. An SAE judged by the Investigator or Clinical Coordinator to have a reasonable causal relationship with the trial medication will be regarded as a Serious Adverse Reaction (SAR). The Clinical Coordinator will also assess all SARs for expectedness. If the event meets the definition of a SAR that is unexpected (i.e. is not defined in the Investigator Brochure) it will be classified as a Suspected Unexpected Serious Adverse Reaction (SUSAR).

8.2.3 Reporting to the Competent Authority and main Research Ethics Committee

8.2.3.1 Suspected Unexpected Serious Adverse Reactions

The Trials Office will report a minimal data set of all individual events categorised as a fatal or life threatening SUSAR to the Medicines and Healthcare products Regulatory Agency (MHRA) and main Research Ethics Committee (REC) within 7 days. Detailed follow-up information will be provided within an additional 8 days.

All other events categorised as SUSARs will be reported within 15 days.

8.2.3.2 Serious Adverse Reactions

The Trials Office will report details of all SARs (including SUSARs) to the MHRA and main REC annually from the date of the Clinical Trial Authorisation, in the form of a Development Safety Update Report.

8.2.3.3 Adverse Events

Details of all AEs will be reported to the MHRA on request.

8.2.3.4 Other safety issues identified during the course of the trial

The MHRA, main REC and drug manufacturer will be notified immediately if a significant safety issue is identified during the course of the trial.

8.2.4 Investigators

Details of all SUSARs and any other safety issue which arises during the course of the trial will be reported to Principal Investigators. A copy of any such correspondence should be filed in the ISF.

8.2.5 Data/Safety Committee

The independent Trial Safety Committee (TSC) will review all SAEs.

